center ethics committee (Comitato Etico Regionale delle Marche - C.E.R.M.) for approval and then registered at ClinicalTrials.gov (NCT04397627). Thereafter, all the participating centers will obtain authorization to participate from the local institutional review board. The results of the study are intended to be presented at national and international medical congresses on corresponding fields of interest (colorectal surgery, abdominal surgery). Written publications of the results are planned within surgical journals. The authorship for written publications is confirmed to all participating investigators, only being granted in the case of substantive contributions to the design, conduct, data analysis, collection and interpretation. Anonymized participant-level datasets will be available after study completion upon reasonable request by contacting the principal investigator.

Statistical Analysis

Quantitative values will be expressed as mean \pm standard deviation (SD), median and range; categorical data with percentage frequencies. For categorical data, analysis will include the use of cross tabulation, chi squared or Fisher's exact test where indicated. Continuous or discrete variables will be analyzed using Student's two-sided t test (allowing for heterogeneity of variances) or with a non-parametric test (Mann-Whitney U test or Kruskal-Wallis test as indicated). Joint and conditional multivariate association between all variables shown to be significant on univariate analysis will be assessed using binary logistic or multiple linear regression. The odds ratio (OR) will be presented followed by 95% confidence interval (95% CI). Concerning comparison of nutritional status scores, areas under the receiver-operating characteristics curve (AUC-ROC) will be calculated for all endpoints, considering values from 0.7 to 0.8 as acceptable, 0.8 to 0.9 excellent, and above 0.9 as outstanding (43). Differences in AUC-ROC curves will be analyzed with the chi-squared test. Optimal cut-off points will be obtained applying Youden's Index (Sensitivity+Specificity-1), choosing those values of the AUC-ROC curve where this index is

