maximal. Negative predictive values (NPV) and positive predictive values (PPV) will also be calculated; finally, a logistic regression model will be built using the presence/absence of endpoint as dependent variable, and nutritional scores \leq or $>$ the cut-off values as explanatory factors; using logistic transformation of the linear predictors, the probabilities of the endpoint related to the different combinations of factors level will be obtained (44). For all statistical tests the significant level is fixed at $p < .05$. Statistical analyses will be carried out using STATA software (Stata Corp. College Station, Texas, USA).

Sample size

Adherence to at least 70% of the ERAS program items was identified as a cut-off for significant improvement of outcomes (18), with a 2:1 expected ratio below:above the cut-off. Estimating a reduction of postoperative PRO from preoperative baseline (1.0) at 0.7 for adherence above the cut-off and at 0.64 for adherence below the cut-off (44), alpha 0.04, beta 0.8, the required sample size is $n=2,406$ (802 cases above 70% adherence and 1,604 below 70% adherence). Reported rates for failure to RIOT and ERAS program items adherence below or above 70% are 13 and 6.5%, respectively (27); the required sample size for evaluation of failure to RIOT is $n=885$ (295 cases above 70% adherence and 590 below 70% adherence). Based on previous iCral observational study on colorectal surgery in Italy (44, 46, 47), the expected ratio of malignant:benign indications to surgery is 70:30 (2,100 resections for malignancy and 900 resections for benign disease on the basis of 3,000 expected cases).

References

2. Kehlet H (2008) Fast-track colorectal surgery. *Lancet* 371:791–793.

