Appendix 2 Mini Nutritional Assessment Short Form (MNA-SF®) (30)

A Presenta una perdita dell' appetito? Ha mangiato meno negli ultimi 3 mesi? (perdita d'appetito, problemi digestivi, difficoltà di masticazione o deglutizione)

- 0 = Grave riduzione dell'assunzione di cibo
- 1 = Moderata riduzione dell'assunzione di cibo
- 2 = Nessuna riduzione dell'assunzione di cibo

B Perdita di peso recente (<3 mesi)

- 0 = perdita di peso > 3 kg
- 1 = non sa
- 2 = perdita di peso tra 1 e 3 kg
- 3 = nessuna perdita di peso

C Motricità

- 0 = dal letto alla poltrona
- 1 = autonomo a domicilio
- 2 = esce di casa

D Nell' arco degli ultimi 3 mesi: malattie acute o stress psicologici?

- 0 = sì 2 = no

E Problemi neuropsicologici

- 0 = demenza o depressione grave
- 1 = demenza moderata
- 2 = nessun problema psicologico

F1 Indice di massa corporea (IMC) = peso in kg / (altezza in m)²

- 0 = IMC <19
- 1 = 19 ≤ IMC < 21
- 2 = 21 ≤ IMC < 23
- 3 = IMC ≥ 23

SE L' IMC NON E' DISPONIBILE, SOSTITUIRE LA DOMANDA F1 CON LA DOMANDA F2.
NON RISPONDERE ALLA DOMANDA F2 SE LA DOMANDA F1 E GIA' STATA COMPLETATA

F2 Circonferenza del polpaccio (CP in cm)

- 0 = CP inferiore a 31
- 3 = CP 31 o superiore

Valutazione di screening (max.14 punti) **12-14** punti: stato nutrizionale normale; **8-11** punti: a rischio di malnutrizione; **0-7** punti: malnutrito.

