Appendix 3 Prognostic Nutritional Index (PNI) (31)

PNI = Serum albumin (g/L) + (0.005 x total lymphocyte count/μL)

Valutazione di screening **≥50**: stato nutrizionale normale; **45-50**: a rischio di malnutrizione; **<45**:malnutrito.

**Appendix 4 Questionario sulla salute – Versione Italiana Euro-QoL Group EQ-5D-5L™ (32)**Data compilazione ____ / ____ / ____ ; preop ; dimissione ; tardivo Sotto ciascun argomento, faccia una crocetta sulla casella (UNA SOLA) che descrive meglio la sua salute OGGI.**CAPACITÀ DI MOVIMENTO**

- Non ho difficoltà nel camminare 5
- Ho lievi difficoltà nel camminare 4
- Ho moderate difficoltà nel camminare 3
- Ho gravi difficoltà nel camminare 2
- Non sono in grado di camminare 1

CURA DELLA PERSONA

- Non ho difficoltà nel lavarmi o vestirmi 5
- Ho lievi difficoltà nel lavarmi o vestirmi 4
- Ho moderate difficoltà nel lavarmi o vestirmi 3
- Ho gravi difficoltà nel lavarmi o vestirmi 2
- Non sono in grado di lavarmi o vestirmi 1

ATTIVITÀ ABITUALI (*per es. lavoro, studio, lavori domestici, attività familiari o di svago*)

- Non ho difficoltà nello svolgimento delle attività abituali 5
- Ho lievi difficoltà nello svolgimento delle attività abituali 4
- Ho moderate difficoltà nello svolgimento delle attività abituali 3
- Ho gravi difficoltà nello svolgimento delle attività abituali 2
- Non sono in grado di svolgere le mie attività abituali 1

DOLORE O FASTIDIO

- Non provo alcun dolore o fastidio 5
- Provo lieve dolore o fastidio 4
- Provo moderato dolore o fastidio 3
- Provo grave dolore o fastidio 2
- Provo estremo dolore o fastidio 1

ANSIA O DEPRESSIONE

[figure not shown]
- Non sono ansioso/a o depresso/a 5
- Sono lievemente ansioso/a o depresso/a 4
- Sono moderatamente ansioso/a o depresso/a 3
- Sono gravemente ansioso/a o depresso/a 2
- Sono estremamente ansioso/a o depresso/a 1

- Vorremmo sapere quanto è buona o cattiva la sua salute OGGI.
- Questa è una scala numerata che va da 0 a 100.
- 100 rappresenta la migliore salute che può immaginare.
0 rappresenta la peggiore salute che può immaginare.
- Segni una X sul punto della scala per indicare com'è la sua salute OGGI.
- Poi, scriva nella casella qui sotto il numero che ha segnato sulla scala numerata.

LA SUA SALUTE OGGI =

La migliore salute
che può
immaginare

La peggiore salute
che può
immaginare

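### Secondary endpoint 8: nutritional-score cut-offs are picked by Youden's index and then used in a logistic model with no allowance for the search, so cut-off-based results are over-optimistic (the AUC comparison is not affected)

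*Protocol*

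**What the plan says.** Secondary endpoint 8 compares MNA-SF and PNI with respect to anastomotic leakage, minor and major complications, and RIOT. The protocol's Statistical Analysis section gives the steps in order:

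1. ROC curves and AUCs are calculated for every endpoint, and the AUCs are compared by a chi-squared test.
2. "Optimal cut-off points will be obtained applying Youden's Index (Sensitivity+Specificity-1), choosing those values of the AUC-ROC curve where this index is" at its maximum.
3. PPV and NPV are calculated.
4. Last, "a logistic regression model will be built using the presence/absence of endpoint as dependent variable, and nutritional scores" at or below versus above those cut-offs serve as explanatory factors. From this model "the probabilities of the endpoint related to the different combinations of factors level will be obtained".

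Two general rules in the same section cover step 4: odds ratios are given with 95% intervals, and "For all statistical tests the significant level is fixed at" p < .05. No split sample, outside data, resampling or adjusted p-value is mentioned.

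The protocol already prints fixed categories for both scores:
- Appendix 2 divides MNA-SF into 12-14, 8-11 ("a rischio di malnutrizione") and 0-7.
- Appendix 3 divides PNI into 50 and above ("stato nutrizionale normale"), 45-50 and below 45.
- Table 1 uses MNA-SF below 12 as a criterion.

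The logistic step uses none of these.

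**The concern.** Maximising Youden's index selects the split that best separates events from non-events in the patients at hand. If that split is then tested in those patients as though it had been set beforehand, part of the apparent effect is only the result of the search. The standard error and p-value take no account of it. The PPV, NPV and predicted probabilities at the chosen cut-off are flattered for the same reason.

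The bias grows with the number of candidate cut-offs. PNI (albumin plus a lymphocyte term) is nearly continuous and MNA-SF is an integer from 0 to 14, so PNI gains more. At stake is a set of cut-offs, odds ratios and risk probabilities that other centres might adopt and that would look weaker in new patients.

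**Working it through.** **Plan's own figure.** The only error rate stated for this step is the nominal 5%. It serves as the benchmark.

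**Inputs from the protocol.** Expected N is 3,000 overall and 2,100 with malignancy (Methods; Sample size). Failure to RIOT is 13% and 6.5% below and above 70% adherence, at a 2:1 ratio, so overall (2 × 13 + 6.5)/3 = 10.8%; 10% was simulated. MNA-SF runs from 0 to 14 in integers; PNI is nearly continuous.

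**Assumptions not in the protocol.** Event rates of 5%, 10% and 25%; PNI roughly normal (mean 48, SD 6); MNA-SF in several shapes, for example a rounded normal (mean 11.5, SD 2.2) clipped to 0-14; correlation between the scores of 0 or 0.4; a low score means risk.

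**Procedure, with the endpoint unrelated to either score.**
- For each score, c* = the value of c that maximises Se(c) + Sp(c) − 1.
- Fit logit P(endpoint) = b0 + b1·I(PNI ≤ c*PNI) + b2·I(MNA-SF ≤ c*MNA).
- Call a score significant if |b/SE(b)| > 1.96. The odds ratio is exp(b).

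**Benchmark reproduced.** With thresholds fixed in advance (MNA-SF < 12, PNI ≤ 45), the joint model gives 4.2-5.9% false positives for PNI and 4.0-5.1% for MNA-SF. The 5% level is recovered, so the search is the cause of what follows.

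**With Youden cut-offs, joint model (1,000 data sets per setting):**

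| Correlation assumed | PNI | MNA-SF | Either score |
|---|---|---|---|
| 0 | 23-24% | 11-12% | 32-33% |
| 0.4 | 15-18% | 6-7% | 21-24% |

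The Monte Carlo standard error near 20% is √(0.2 × 0.8/1,000) = 1.3 points. A repeat with 1,500 data sets per setting (N and event rate 3,000/5%, 2,100/10%, 3,000/25%) gave:
- correlation 0: PNI 23-26%, MNA-SF 10-12%, either score 32-33%;
- correlation 0.4: PNI 17-20%, MNA-SF 6-7%, either score 22-26%;
- median PNI odds ratio 1.16-1.37, where the truth is 1.00.

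**Each score tested alone.** PNI 22-25% (Wald or Pearson) and 24-27% (likelihood ratio). MNA-SF 8-15%, depending on how many levels are well filled.

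**With a true effect.** For the PNI-like score, apparent odds ratio against the odds ratio of the same cut-off in fresh patients:

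| True log-odds per SD | Apparent | Fresh | Ratio |
|---|---|---|---|
| 0.1 | 1.52 | 1.18 | 1.29 |
| 0.2 | 1.69 | 1.39 | 1.22 |
| 0.4 | 2.22 | 1.91 | 1.16 |

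The relative inflation shrinks as the real effect grows but does not vanish. Optimism in PPV, NPV and predicted probabilities was not quantified; its direction follows from the same selection.

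**The case against.** **The comparison of the scores rests on AUC.** A reader might infer that the comparison of MNA-SF with PNI is itself tilted toward PNI. The protocol does not support that. It compares the scores by AUC, which uses no cut-off, and it states no test between the two scores' odds ratios or predictive values. This objection stands. Only the cut-off-based results are affected.

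**The size depends on the model.** A reader might quote a false-positive rate of 10-27%. That describes each score tested alone. The plan derives probabilities for combinations of the factors, which points to both scores in one model. There the MNA-SF rate can be close to nominal if the scores are correlated, as two measures of nutritional status may well be. This also stands, and it is why the joint-model range is the one to report. In every setting examined, PNI remains at least about three times nominal.

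**The model's purpose is prediction.** Its stated output is probabilities, and no decision hangs on its p-value. That is fair, but the general rules on intervals and significance still cover it, and the probabilities come from the same inflated coefficients.

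**A SAP could add validation.** True: reuse of the same patients is inferred from the absence of any other dataset. The point, however, is the sequence that the protocol does state, which would need amending in any case.

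**The appendix thresholds classify malnutrition, not surgical outcome, and there are two per score.** Correct. Looking for outcome-specific cut-offs is a legitimate exploratory aim, and any fixed threshold has to be named.

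**Conclusion.** The concern holds for the cut-off-based part of secondary endpoint 8. Followed as written, with no true association, the plan gives a joint-model false-positive rate of about 15-25% for PNI and about 5-12% for MNA-SF, against 5% per coefficient. At least one score is significant in about 20-35% of studies. The median spurious PNI odds ratio is about 1.15-1.4. These figures are simulated and rest on assumed event rates, score distributions and correlation, with low scores taken as the risk direction. If the direction were also read from the data, PNI tested alone would reach 38-41%; the protocol does not say that this will be done.

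The odds ratios, intervals, PPV, NPV and predicted probabilities are over-optimistic, more so for PNI. The AUC comparison, both primary endpoints and both sample sizes are untouched. The change should be made, but the main conclusions of the study do not depend on it.

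**What to change.** Amend the Statistical Analysis section as follows:

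- In the logistic model, enter both scores as continuous terms. Alternatively, dichotomise at thresholds fixed before analysis, taken from the appendix categories and named explicitly, for example MNA-SF < 12 (already used in Table 1) and PNI < 45.
- Report Youden cut-offs, and every odds ratio, PPV, NPV and probability derived from them, as exploratory. Attach a bootstrap optimism correction that repeats the cut-off search in each resample.
- Keep the AUC comparison as planned.

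The cost is a change of wording and a bootstrap loop, with no new data, patients or visits. The reported accuracy will look somewhat less favourable.

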Prospective enrollment from November 2020 to October 2021 in 60 Italian surgical centers. All patients undergoing elective or delayed urgency colorectal surgery with anastomosis will be included in a prospective database after written informed consent. A total of 3,000 patients is expected based on a mean of 50 cases per center.

Inclusion criteria

1. Patients submitted to laparoscopic/robotic/open/converted ileo-colo-rectal resection with anastomosis, including planned Hartmann's reversals.
2. American Society of Anesthesiologists' (ASA) class I, II or III
3. Elective or delayed urgency surgery
4. Patients' written acceptance to be included in the study.

Exclusion criteria

1. American Society of Anesthesiologists' (ASA) class IV-V
2. Emergent surgery
3. Pregnancy
4. Hyperthermic intraperitoneal chemotherapy for carcinomatosis.

Outcome measures

1. Preoperative risk factors for morbidity (age, gender, obesity, nutritional status, diabetes, cardiovascular disease, chronic liver disease, renal failure, inflammatory

bowel disease, perioperative steroid therapy, ASA class I-II vs III, SARS-CoV-2 infection)

2. Operative parameters (approach, procedure, anastomotic technique, length of operation, pTNM stage)
3. Adherence to ERAS program (28, 29) items (Tab.1).

Endpoints

Primary

1. Patient-related outcomes measures (PROMs):
 - a. Euro-QoL Group EQ-5D-5L (EQ-5D-5L, 32);
 - b. MD Anderson Symptom Inventory for gastrointestinal surgery patients (MDASI-GI, 33);
 - c. Functional Assessment of Cancer Therapy – Colorectal (FACT-C, 34)
2. Return to intended oncologic therapy (RIOT, 24)

Secondary

3. Anastomotic leakage rate
4. Minor and major complication rates according to Clavien-Dindo (35, 36) and JCOG (37) classification
5. Overall length of postoperative hospital stay (including any readmission)
6. Difference between date of readiness for discharge (RFD, 38) and date of actual discharge
7. Readmission and reoperation rates
8. Comparison of two nutritional status scores, MNA-SF (30) and PNI (31), regarding anastomotic leakage, minor and major complication rates and RIOT (24)

9. Impact of anastomotic testing through air-leak test (ALT) and near-infrared fluorescence (NIR) narrow-band imaging (NBI) using indocyanine green (ICG) on anastomotic leakage rates

Recorded data and follow-up

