Anastomotic dehiscence (any deviation from the planned postoperative course related to the anastomosis, or presence of pus or enteric contents within the drains, presence of abdominal or pelvic collection in the area of the anastomosis on postoperative CT scan, leakage of contrast through the anastomosis during enema or evident anastomotic dehiscence at reoperation for postoperative peritonitis) will be defined and graded according to international consensus guidelines (41). Anastomotic testing will be performed intraoperatively with the air-leak test (ALT) and using ICG-NIR-NBI with a standard protocol [*ICG 25 mg diluted in 10 mL water (2.5 mg/mL); first bolus i.v. injection of 4 mL (10 mg) after vascular control and mesenteric division, just before proximal and/or distal bowel division; second bolus i.v. injection of 4 mL (10 mg) just before joining anastomotic stumps; third (optional) bolus i.v. injection of 2 mL (5 mg) after the anastomosis is completed; NIR-NBI observation within 120-180" after every ICG injection (direct, laparoscopic or endoscopic)*].

PROM questionnaires (32-34) will be administered to all enrolled patients four to one week before the planned operation, on the day of discharge, and 6 weeks after the operation.

RIOT (24) rates will be recorded in all patients submitted to surgery for malignancy, according to national guidelines for colorectal cancer (42).

After anonymization, all data of each single case will be prospectively uploaded by local investigator(s) on a protected web-based database and incorporated into a spreadsheet for data analysis, checking for any discrepancy, that will be addressed and solved through strict cooperation between chief investigator, data manager and participating centers.

Ethics and dissemination

The study will be conducted according to the Helsinki declaration and to the Guideline for good clinical practice E6(R2) principles. This study protocol will be submitted to the coordinating
ALL 3 – Protocollo dello Studio

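### The study is sized at alpha 0.04 but tested at p<.05 throughout, and four named primary endpoints share that threshold with no primary instrument, time point or error control

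*Protocol*

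**What the plan says.** - **Threshold for analysis** (Protocol, Statistical Analysis): "For all statistical tests the significant level is fixed at" p<.05. No test is exempted and no adjustment is mentioned.
- **Threshold for planning** (Protocol, Sample size): "alpha 0.04, beta 0.8, the required sample size is $n=2,406", split as 802 above and 1,604 below 70% adherence. The RIOT size, 885 (295 and 590), follows in the next sentence, which prints no alpha of its own.
- **Primary endpoints** (Protocol, Endpoints): item 1 is headed "Patient-related outcomes measures (PROMs") and lists EQ-5D-5L, MDASI-GI and FACT-C. Item 2 is RIOT. That makes four named primary endpoints under two headings.
- **Timing** (Protocol, Recorded data and follow-up): the questionnaires are given before surgery, then "on the day of discharge, and 6 weeks after the operation".
- **Not fixed anywhere:** which questionnaire, which score or which postoperative time is the primary one. The sample-size paragraph speaks only of postoperative PRO. There is no alpha split, no order of testing and no rule for what counts as a positive primary result.

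**The concern.** Two points meet here. First, one document gives two significance levels, so the type I error for which the study was sized is not the one it will use. Second, the stated rule gives each primary endpoint its own full 5% threshold and leaves the questionnaire and the time point open. Any one of several results could then be reported as the positive primary outcome, with a chance of a false claim well above the nominal 5%. At stake is whether a primary claim about ERAS adherence can be read at its stated error rate.

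**Working it through.** **1. Reproduce the stated sizes.** The protocol prints no formula, so one has to be inferred.

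Inputs from Sample size:
- PRO: "at 0.7 for adherence above the cut-off and at 0.64 for adherence below the cut-off (44). No standard deviation is given, so 0.70 and 0.64 are treated as proportions.
- Failure to RIOT: 6.5% above and 13% below the cut-off.
- Ratio below:above k = 2, alpha 0.04. The 0.8 printed as beta works only as power.
- Two-sided testing is assumed. The Statistical Analysis section says so only for the t test ("Student's two-sided t test (allowing for heterogeneity of variances").

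Formula for the smaller group, with pooled p = (p1 + 2·p2)/3 and d = |p1 − p2|:

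n = [z(1−α/2)·√(1.5·p(1−p)) + z(power)·√(p1(1−p1) + p2(1−p2)/2)]² / d²

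Continuity correction: n' = (n/4)·[1 + √(1 + 6/(2·n·d))]². Total = 3·n', with n' rounded up.

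PRO at 0.04: p = 0.66, z = 2.0537 and 0.8416.
- n = (1.1915 + 0.4799)²/0.0036 = 776.1
- n' = 800.9, rounded up to 801; total 2,403

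RIOT at 0.04: p = 0.1083.
- n = (0.7818 + 0.2883)²/0.065² = 271.0
- n' = 293.6, rounded up to 294; total 882

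| Two-sided alpha, 80% power | PRO total | RIOT total |
|---|---|---|
| Stated in the protocol | 2,406 | 885 |
| 0.04, with correction | 2,403 | 882 |
| 0.05, with correction | 2,256 | 828 |
| 0.04, without correction | 2,331 | 816 |

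Each stated total is 3 above the 0.04 result, that is, one more patient in the smaller group. A one-sided 0.05 with 90% power also comes fairly close (2,442 and 876), but it contradicts the printed 0.04 and 0.8.

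**2. Does the mismatch cost power?** Power at the stated sizes (same formula, no continuity correction):

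| Tested at | PRO, 2,406 | RIOT, 885 |
|---|---|---|
| 0.04 | 81.3% | 83.6% |
| 0.05 | 83.8% | 86.0% |

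Power rises slightly.

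**3. Chance of at least one false primary claim**, all null hypotheses true, each test at 0.05.

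Independent tests: 1 − 0.95^m.
- m = 2 (one questionnaire and RIOT): 1 − 0.9025 = 9.8%
- m = 4 (each named endpoint once): 18.5%
- m = 7 (three questionnaires × two postoperative times, plus RIOT): 30.2%

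The document gives no correlations. They are therefore assumed: questionnaire tests equally correlated, RIOT independent, 400,000 simulated draws.

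| Correlation | Four tests | Seven tests |
|---|---|---|
| 0.3 | 17.9% | 27.9% |
| 0.5 | 17.0% | 24.8% |
| 0.7 | 15.3% | 20.6% |
| 0.9 | 13.0% | 15.3% |

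Using 0.04 per test would not cure this: with independent tests it gives 15.1% for four (1 − 0.96^4) and 24.9% for seven (1 − 0.96^7).

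**4. Size under a controlled two-test family.** At 0.025 each, the formula of step 1 gives 3 × 906 = 2,718 (PRO) and 3 × 332 = 996 (RIOT). The protocol expects 3,000 patients, 2,100 of them with malignancy. The PRO margin is 3,000 − 2,718 = 282, or 9.4%. Bonferroni over all four endpoints (0.0125 each) would need 3,177 for PRO, above the expected 3,000.

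**The case against.** **The count of tests.** A reader might infer that the primary family holds at least seven tests. The documents do not say so. The schedule states when questionnaires are given, not that each postoperative score is a primary test. The Background closes with two objectives (PRO and failure to RIOT), and Sample size treats PRO as a single quantity. Four endpoints are named; seven is one possible reading. This objection stands, and it widens the error range downward to about 10%.

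**Harm from 0.04 against 0.05.** A reader might infer that the study is underpowered at the threshold it will apply. It is not: step 2 shows a small gain. The mismatch alone is an inconsistency to correct.

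**An alpha split.** The 0.04 might be taken as one share of a divided 0.05. The RIOT size also reproduces at the full 0.04, and 0.04 + 0.04 exceeds 0.05. Because the RIOT sentence prints no alpha and the formula is inferred, this is a well-supported reading rather than a stated fact.

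**Left to a SAP.** A multiplicity procedure is often placed there, and the SAP is not at hand. That would answer a silent protocol. This protocol states a rule, p<.05 for every test, and a SAP could add control for the primary tests only by departing from it.

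**Separate questions, separate populations.** PRO concerns all patients and RIOT only those with malignancy, so joint control over the two can be debated. Even if each objective kept its own 5%, the three questionnaires and two times within PRO would remain uncontrolled.

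**No extra patients needed.** It is tempting to say that 3,000 covers 2,718. That figure treats a questionnaire score as a proportion, although the analysis section plans t or rank tests for continuous or discrete variables. The 3,000 is itself an expectation (60 centers, mean 50 cases). No attrition figure is given, and a loss above 9.4% would remove the margin.

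**Conclusion.** The point holds, and the plan is wrong as written in two respects. The two significance levels contradict each other and must be reconciled. The blanket p<.05 over four named primary endpoints, with no primary questionnaire or time point, puts the chance of a false primary claim at about 10% (one questionnaire plus RIOT), 13% to 19% (four tests) or 15% to 30% (seven tests). On every reading this is roughly two to six times the nominal 5%.

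These figures assume that all null hypotheses are true, that questionnaire tests correlate equally between 0 and 0.9, and that RIOT is independent of them. The conclusion about 0.04 rests on a back-calculated formula that matches both stated sizes within 3 patients.

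**What to change.** Before the data are analysed:

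1. Name one questionnaire score and one postoperative time point as the primary PRO endpoint. The choice is the investigators'; 6 weeks is one option. Make the other questionnaire scores and times secondary.
2. Test this endpoint and RIOT as a family of two held at 0.05, by Holm or at 0.025 each, and say so in Statistical Analysis in place of the blanket rule. Keep unadjusted p<.05 only for secondary tests, labelled exploratory.
3. Use the same alpha in Sample size, state it for RIOT as well, and restate either the two sizes or the power at the expected 3,000 (2,100 with malignancy). Relabel the 0.8 as power.
4. If the implied two-proportion calculation is kept, quote 2,718 (PRO) and 996 (RIOT) as indicative only, and state the allowance for missing questionnaires.

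The cost is mainly wording. Each primary test faces a stricter threshold, and stated power falls somewhat: at 0.025 the stated 2,406 and 885 give 75.8% and 77.9% by the uncorrected calculation of step 2. Whether 3,000 is enough for the PRO endpoint depends on questionnaire completion, for which the protocol gives no figure.

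### The patient-reported outcome sample size of 2,406 matches a two-proportions calculation, but the endpoint as described is a score and no SD is given, so the stated size and power do not belong to the planned comparison.

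*Protocol*

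**What the plan says.** The Sample size section of the protocol divides patients at 70% adherence to the ERAS items, "with a 2:1 expected ratio below:above the cut-off". For the first primary endpoint it proceeds by "Estimating a reduction of postoperative PRO from preoperative baseline (1.0) at 0.7 for adherence above the cut-off". Patients with lower adherence are assigned a value of 0.64 on the same scale. The error rates are given as "alpha 0.04, beta 0.8". The result is 2,406, made up of "802 cases above 70% adherence and 1,604 below 70% adherence". No SD appears and no formula is named.

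The same paragraph sizes the second primary endpoint, failure to return to intended oncologic therapy (RIOT). It uses rates of 13% and 6.5% and obtains 885 patients (295 above and 590 below the cut-off).

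The Endpoints list gives the PRO endpoint as three questionnaires: EQ-5D-5L, MDASI-GI and FACT-C. Appendices 4 to 6 show multi-item numeric scales. No responder or recovery threshold is set for any of them.

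The Statistical Analysis section assigns tests by type of variable. Categorical data get chi-squared or Fisher's exact test. Continuous or discrete variables get "two-sided t test (allowing for heterogeneity of variances) or with a non-parametric test".

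The Methods section separately expects 3,000 patients, from 60 centres with an average of 50 cases each.

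**The concern.** Sizing a comparison of scores requires the spread of the score. The PRO sentence gives two levels, an alpha, a beta and an allocation ratio, which is a complete set of inputs for comparing two proportions but one short for comparing two means. If 0.70 and 0.64 were entered as though they were shares of patients, the 2,406 and the power attached to it describe a test on an endpoint that the protocol does not contain. A reader could not then tell what power the planned PRO comparison has.

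The beta adds to this. Beta is the type II error rate, so a beta of 0.8 means 20% power.

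**Working it through.** **Inputs** (Sample size section unless noted): p1 = 0.70 (above the cut-off, smaller group); p2 = 0.64 (below); difference d = 0.06; ratio k = 2; alpha = 0.04; power = 0.80, reading the stated beta as power. Two-sidedness is not stated there and is taken from the Statistical Analysis section ("Student's two-sided t test (allowing for heterogeneity of variances"). Normal quantiles: z(0.98) = 2.054 and z(0.80) = 0.842, sum 2.895.

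**1. Reproducing 2,406 as a comparison of proportions.**

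Pooled proportion: (0.70 + 2 × 0.64)/3 = 0.66.

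Uncorrected size of the smaller group:

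n = [2.054 × √(1.5 × 0.66 × 0.34) + 0.842 × √(0.70 × 0.30 + 0.64 × 0.36/2)]² / 0.06² = (1.1915 + 0.4799)² / 0.0036 = 776.1, rounded up to 777.

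Continuity correction:

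n' = (n/4) × [1 + √(1 + 2(k + 1)/(n·k·d))]² = (777/4) × [1 + √(1 + 6/(777 × 2 × 0.06))]² = 801.8, rounded up to 802.

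The larger group is 2 × 802 = 1,604 and the total is 2,406. This is exact. Without rounding 776.1 up first, the result is 801 and 2,403.

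**2. Cross-check on RIOT.** With 6.5% versus 13%, the same steps give 271.0 uncorrected (272 rounded up) and 294.6 corrected. That is 295, 590 and a total of 885, again exact.

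**3. Variants that miss** (PRO total):

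| Variant | Total |
|---|---|
| No continuity correction | 2,331 |
| Unpooled variance | 2,274 |
| Arcsine | 2,313 |
| One-sided alpha 0.04, without / with correction | 1,866 / 1,941 |
| Two-sided alpha 0.05, without / with correction | 2,181 / 2,256 |

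**4. The stated beta.** Taking beta = 0.8 literally (power 0.20), step 1 needs only about 165 in the smaller group, not 802. The printed figure therefore belongs to power 0.80.

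**5. The SD at which a two-means formula gives the same size.**

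SD = 0.06 / [2.895 × √(1/802 + 1/1,604)] = 0.06 / (2.895 × 0.04325) = 0.479.

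The SD of a yes/no variable is √(0.70 × 0.30) = 0.458 at 0.70 and √(0.64 × 0.36) = 0.480 at 0.64. The implied SD is essentially that of a binary variable.

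**6. What a comparison of means would need and deliver.** The SDs are assumptions on the scale where baseline is 1.0, because the protocol gives none. The difference is 0.06 and alpha is 0.04, two-sided.

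Smaller group: n = 2.895² × SD² × 1.5 / 0.06², total 3n.

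Power: Φ(0.06 / [SD × √(1/n1 + 1/n2)] − 2.054).

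| Assumed SD | Total for 80% power | Power at 802/1,604 | Power at 1,000/2,000 |
|---|---|---|---|
| 0.2 | 420 | >0.99 | >0.99 |
| 0.3 | 945 | >0.99 | >0.99 |
| 0.4 | 1,677 | 0.92 | 0.97 |
| 0.5 | 2,622 | 0.76 | 0.85 |
| 0.6 | 3,774 | 0.60 | 0.70 |

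The last column is the 3,000 expected, split 2:1 with complete PRO data. There, power falls below 0.80 only when SD exceeds 0.06 / (2.895 × √(1/1,000 + 1/2,000)) = 0.535.

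**The case against.** Four points can be made for the protocol.

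- **The study is probably large enough.** This stands. The 3,000 comes from centre capacity, not from this calculation, and it exceeds 2,406. A score confined to 0–1 with mean 0.70 or 0.64 cannot have an SD above 0.458 or 0.480, so the proportions formula is close to its worst case. SDs of 0.5 or 0.6 arise only if some patients score above their own baseline, which a ratio to baseline allows. A reader might infer that the PRO comparison is underpowered or that the enrolment target collapses. The protocol supports neither.
- **The formula is inferred, and the text never says mean.** This also stands. A two-means formula with SD 0.479 gives the same number, and the cited source for the two values is not available here. However, the text describes a PRO level against a baseline of 1.0, and one routine returns both printed sample sizes to the patient. The inference is strong, though it is not proof.
- **A binary PRO endpoint may be intended.** It might be, and the Statistical Analysis section does provide chi-squared and logistic regression. But no such endpoint is defined, and the questionnaires are listed as instruments without a threshold.
- **The beta is only a slip of labelling.** Agreed. It did not affect the number, but it is wrong as printed.

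Nor can the matter simply be left to a statistical analysis plan: the protocol itself prints a required size and its inputs, and these do not fit the endpoint it describes.

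**Conclusion.** The point holds as a misfit between calculation and endpoint. The arithmetic behind 2,406 is right for two proportions of 0.70 and 0.64 at two-sided alpha 0.04 and 80% power. The endpoint as described is a score, so 2,406 and its power are not properties of the planned comparison unless the SD happens to be about 0.479, and the protocol gives no support for that value.

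The practical size cannot be fixed without an SD. For assumed SDs from 0.2 to 0.6, the requirement runs from 420 to 3,774. At the 3,000 expected, power runs from above 0.99 to 0.70 and stays at or above 0.80 up to an SD of about 0.535. This assumes one unadjusted comparison, the 2:1 split, complete questionnaires and alpha 0.04. The conclusion is that the stated power is unsupported, not that the study is too small.

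**What to change.** Keep the 3,000. In the Sample size section, do one of the following:

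- **If 0.70 and 0.64 are scores:** replace the PRO calculation with a two-means calculation for one named questionnaire and time point. State the difference, the SD with its source and the two-sided alpha, then give the power or the detectable difference at 3,000. At 1,000/2,000, alpha 0.04 and 80% power, the detectable difference is 2.895 × 0.03873 × SD, or about 0.112 × SD. That is 0.034 at an assumed SD of 0.3 and 0.056 at 0.5. A baseline-adjusted (ANCOVA) version is optional.
- **If they are proportions of patients:** define the binary PRO endpoint, with its threshold and time point, and name the chi-squared test for it. The 2,406 can then stand.

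In either case, replace the stated beta with power 0.80 (beta 0.20) and name the formula used.

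The cost is a rewritten paragraph and a search for a usable SD, with no added patients. The restated power may turn out higher or lower than 80%.
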